Appendix 1-A (cont.) Schedule of Assessments

	Schedule of Assessments—Arm D																			Study Comp/ET ^c	Early Disc. Safety F/U Visit before Study Comp ^d
	Screen-ing ^a	Wk 1	Wk 2	Wk 3	Wk 4	Wk 5	Wk 7	Wk 9	Wk 13	Wk 17	Wk 21	Wk 25	Wk 29	Wk 33	Wk 37	Wk 41	Wk 49	Q12W from Wk 61	Daily/weekly ^b		
Informed consent ^e	x																				
Inclusion/exclusion criteria	x																				
Medical history and demographics ^f	x																				
Physical examination (including weight) ^g	x					x			x			x			x		x	x		x	x
Height	x											x					x				
Vital signs ^h	x	x	x	x	x	x	x	x	x	x	x	x	x	x	x	x	x	x	x	x	
Serum pregnancy test ⁱ	x	x																			
Urine pregnancy test ⁱ		x			x		x	x	x	x	x	x	x	x	x	x	x	x	x	x	
Concomitant medications ^j		x	x	x	x	x	x	x	x	x	x	x	x	x	x	x	x	x	x	x	
ECG ^k	x	x			x															x	
Safety laboratory assessments ⁱ	x		x		x			x	x	x	x	x	x	x	x	x	x	x	x	x	
Bleed/medication questionnaire ^l																			x	x	x
Bleed/medication data review ^s		x			x		x	x	x	x	x	x	x	x	x	x	x	x	x	x	
Adverse events ^m		x	x	x	x	x	x	x	x	x	x	x	x	x	x	x	x	x	x	x	
IMP management ⁿ		x	x	x	x	x	x	x	x	x	x	x	x	x	x	x	x	x	x	x	
Haemo-QoL-Short Form ^o	x							x			x			x		x		x		x	
Adapted Inhib-QoL ^o	x							x			x			x		x		x		x	
Emicizumab administration ^p		x	x	x	x	x	x	x	x	x	x	x	x	x	x	x	x	x	x		
PK/PD/ADA assessment ^q		See Appendix 2-A for details.																			
Following treatment with bypassing agents ^r		Monitoring for thromboembolic events and thrombotic microangiopathy ^r																			

Appendix 1-A (cont.) Schedule of Assessments

Disc =discontinuation; eCRF=electronic Case Report Form; ET=early termination; F/U=follow-up; FVIII=factor VIII; HRQoL=health-related Quality of Life; IMP=investigational medicinal product; Adapted Inhib-QoL =Inhibitor-Specific Quality of Life (with Aspects of Caregiver Burden); PD=pharmacodynamic; PK=pharmacokinetic; Q8W=every 8 weeks; Q12W=every 12 weeks; study comp.=study completion; Wk=week.

Notes: All assessments should be performed within \pm 2 days of the scheduled visit for the first 3 months, then \pm 7 days thereafter. PD and PK (trough) samples will be collected within \pm 2 days of the scheduled visit and linked to the timing from the dose. Clinic visits should coincide with the day of emicizumab dosing, and on those days the dose should be administered after blood draws and other assessments are conducted.

Unscheduled assessments may be performed at the discretion of the investigator and as clinically indicated. Except for the bleed/injection questionnaire, HRQoL, and health status, all other patient data will be collected during office or nurse visits. Evaluation at Week 25 or 49 will occur after a full 24 or 48 weeks in the study, respectively. Study completion evaluation occurs when a patient discontinues emicizumab or transitions into another study.

- ^a Screening may occur up to 4 weeks before Week 1 dosing.
- ^b Patients will complete the bleed/medication questionnaire at least weekly and at the time of a bleed, or when they take a hemophilia-related medication (including emicizumab). Arm B patients should indicate at least weekly whether or not they had a bleed.
- ^c There will be an Extension Phase in this study for all patients who have completed at least 52 weeks of treatment with prophylactic emicizumab and are still deriving clinical benefit. The study will be extending for 3 years after the last Arm D patient completes 1 year of treatment *and patients still having clinical benefit are transferred to a post-trial continued access solution per Roche Global Policy on Continued Access to Investigational Medicinal Products (Section 4.3.4). The study will end earlier, before 3 years after the last Arm D patient completes 1 year treatment, should the post-trial continued access solution be available earlier.*
- ^d In the event a patient discontinues emicizumab early before the study completion, an early discontinuation safety follow-up visit should be performed 24 weeks after discontinuation of emicizumab. *If a patient enters extension phase, follow Appendix 1-B for study completion or early discontinuation safety follow up.*
- ^e Obtain written informed consent (or patient's assent and caregiver written informed consent if patient is an adolescent/pediatric) before distribution of electronic, handheld device and collection of any data. Patients will be enrolled and randomized after giving informed consent, and assent when appropriate.
- ^f Collected from patient medical records and documented on the eCRF, including information on target joint(s).
- ^g Calculation of dose based on weight is required. A complete physical examination will be performed at screening and at least a targeted physical examination will be performed at subsequent visits. Targeted physical examination of joints (for bleeds, evidence of arthropathy) and skin (for bruises, hematomas, and injection-site reactions) as clinically indicated and/or with report of new or worsening adverse event.
- ^h Body temperature (oral or tympanic), blood pressure, pulse rate, and respiratory rate only to be used to monitor hypersensitivity reactions during and after injection and not to be entered on eCRF, except at Weeks 1, 25, 49, study completion/early termination, and at the Early Discontinuation Safety Follow-up visit before study completion (i.e., 24 weeks after discontinuing emicizumab for patients in Arms A and B and at Week 73 for patients in Arm C). Weight will be measured and recorded in the eCRF at each clinic visit prior to any injections (if applicable.) Height will be measured at screening and annually.

Appendix 1-A (cont.) Schedule of Assessments

- ⁱ Laboratory data (performed locally) include: complete blood count with differential (i.e., neutrophils, hemoglobin, platelet count), serum chemistries (i.e., sodium, potassium, glucose, blood urea nitrogen, creatinine, calcium, phosphorus, magnesium, total and direct bilirubin, albumin, alanine aminotransferase, aspartate aminotransferase, and alkaline phosphatase). Laboratory assessments completed at the screening visit do not have to be repeated at Week 1, if the period between screening and Week 1 is 5 days or less and there has been no change in health status as assessed by the investigator. Patients with childbearing potential will be required to have a negative serum pregnancy test result at screening (and within 7 days of study drug initiation, if applicable) and urine pregnancy tests performed at every clinic visit, with the exception of Weeks 2–4 and 7. Patients on Arm C will have urine pregnancy test performed at screening and before starting emicizumab (Week 25).
- ^j Concomitant medications (e.g., extra pain medication with bleed) will be asked about at the time of the monthly assessment, excluding treatments for bleeds (i.e., FVIII and other medications to treat bleeds), which will be collected on the bleeding questionnaire.
- ^k Performed locally. If screening ECG is abnormal, repeat at Week 1 (or Week 2 if screening and Week 1 occur on the same day), otherwise do not repeat. ECGs will also be performed 4–8 and 24 weeks after starting emicizumab or dose up-titration, as well as at study completion/early termination.
- ^l Reported by the patient or their caregivers and includes: start date and time, reason, type, location, and associated symptoms for joint and muscle bleeds, as well as start date and time, reason, type, and dose of each injection, excluding emicizumab.
- ^m Injection-site reaction adverse events will be collected on a separate form from the adverse event form. If there is unexpected worsening of the patient's hemophilia in terms of severity (e.g., increased number of doses of FVIII to stop bleeds compared with before study entry), frequency of bleeds, or nature at any time during the study, this should be documented as an adverse event on the Adverse Event eCRF, conveying that the underlying condition has changed by including applicable descriptors (e.g., "increased clinical severity of hemophilia").
- ⁿ Drug accountability will not be performed at the first visit that includes emicizumab receipt. Drug dispensation will not occur at the study completion/early termination visit.
- ^o Patient-reported outcomes will be captured on-site by a device and transmitted to the patient-reported outcome database. The questionnaires should be completed by the patient or their caregivers at the site at the start of the visit and prior to all other study assessments. For patients in Arms A, B and C, questionnaires include Haem-A-QoL questionnaire (age ≥ 18 years) and Haemo-QoL-Short Form (age 12–17 years), and health status questionnaire EQ-5D-5L. For patients from Arm D and their caregivers, questionnaires include Haemo-QoL-Short Form (age 8–12 years) and Adapted InhibQoL including Aspects of Caregiver Burden (completed by caregivers, regardless of age). Days of work/school missed will be captured, as applicable to each arm.
- ^p For patients randomized to Arm A: emicizumab prophylaxis at 3 mg/kg QW subcutaneously for 4 weeks, followed by 1.5 mg/kg QW subcutaneously. For patients randomized to Arm B: emicizumab prophylaxis at 3 mg/kg QW subcutaneously for 4 weeks, followed by 6 mg/kg Q4W subcutaneously. For patients randomized to Arm C, following 24 weeks of no prophylaxis: emicizumab prophylaxis at 3 mg/kg QW subcutaneously for 4 weeks, followed by 6 mg/kg Q4W subcutaneously. For patients in Arm D: emicizumab prophylaxis at 3 mg/kg QW subcutaneously for 4 weeks, followed by 1.5 mg/kg QW subcutaneously. There will be an extension phase in this study for all patients who complete at least 52 weeks of treatment with prophylactic emicizumab and still deriving clinical benefit. The study will be extending for 3 years after the last Arm D patient completes 1 year of treatment or until China's reimbursement of emicizumab is received, whichever comes first *and patients still having clinical benefit are transferred to a post-trial continued access solution per Roche Global Policy on Continued Access to Investigational Medicinal Products (see Section 4.3.4)*. The study will end earlier, before 3 years after the last Arm D patient completes 1 year treatment, should the post-trial continued access solution be available earlier.

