4.5.1 Informed Consent Forms and Screening Log

Written informed consent for participation in the study must be obtained from the parent/legally acceptable representative and an Assent from the child when applicable before performing any study-specific screening tests or evaluations. Informed Consent Forms for enrolled patients and for patients who are not enrolled will be maintained at the study site. For adolescents (i.e., 12–17 years of age), an Informed Assent Form will be completed instead. Parents or legally authorized representatives of pediatric patients and adolescents will also complete an Informed Consent Form.

All screening evaluations must be completed within 4 weeks prior to the first dose and reviewed to confirm that patients meet all eligibility criteria before enrollment and randomization. The investigator will maintain a *detailed* record of all patients screened and to *document* eligibility or record reasons for screening failure, as applicable.

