Appendix 1-A Schedule of Assessments

Schedule of Assessments—Arms A and B																		
	Screen-ing ^a	Wk 1	Wk 2	Wk 3	Wk 4	Wk 5	Wk 7	Wk 9	Wk 13	Wk 17	Wk 21	Wk 25	Q8W from Wk 33	Wk 49	Q12W from Wk 61	Daily/weekly ^b	Study Comp/ET ^c	Early Disc. Safety F/U Visit before Study Comp ^d
Informed consent ^e	x																	
Inclusion/exclusion criteria	x																	
Medical history and demographics ^f	x																	
Physical examination (including weight) ^g	x	x				x					x		x			x	x	
Height	x										x		x					
Vital signs ^h	x	x ^h	x	x	x	x	x	x	x	x	x ^h	x	x ^h	x		x ^h	x	
Serum pregnancy test ⁱ	x	x																
Urine pregnancy test ⁱ		x			x		x	x	x	x	x	x	x	x		x	x	
Concomitant medications ^j	x	x			x		x	x	x	x	x	x	x	x		x	x	
ECG ^k	x	x ^k			x						x					x		
Safety laboratory assessments ⁱ	x ⁱ	x	x	x	x	x	x	x	x	x	x	x	x	x		x	x	
Bleed/medication questionnaire ^l															x			
Bleed/medication data review ^l		x			x		x	x	x	x	x	x	x	x		x	x	
Adverse events ^m		x	x	x	x	x	x	x	x	x	x	x	x	x		x	x	
IMP management ⁿ		x	x	x	x	x	x	x	x	x	x	x	x	x		x		
HRQoL and health status (EQ-5D-5L) ^o		x							x			x		x		x		
Emicizumab administration ^p		x	x	x	x	x	x	x	x	x	x	x	x	x	x	x		
PK/PD/ADA assessment ^q	See Appendix 2-A for details																	
Following treatment with bypassing agents ^r	Monitoring for thromboembolic events and thrombotic microangiography ^r																	

Emicizumab—F. Hoffmann-La Roche Ltd

114/Protocol YO39309, Version 5

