Appendix 1-A (cont.) Schedule of Assessments

Schedule of Assessments—Arm C (Screening to Switch to Emicizumab)								
	Screening ^a	Wk 1	Wk 5	Wk 9	Wk 13	Wk 17	Wk 21	Daily/weekly ^b
Informed consent ^e	x							
Inclusion/exclusion criteria	x							
Medical history and demographics ^f	x							
Physical examination (including weight) ^g	x	x						
Vital signs ^h	x	x ^h	x	x	x	x	x	
Height	x							
Serum pregnancy test ⁱ	x	x						
Urine pregnancy test ⁱ		x						
Concomitant medications ^j	x	x	x	x	x	x	x	
ECG ^k	x	x ^k						
Safety laboratory assessments ⁱ	x ⁱ	x						
Anti-FVIII antibodies	x							
Bleed medication questionnaire ^l								x
Bleed/injection data review ^s		x	x	x	x	x	x	
Adverse events ^m		x	x	x	x	x	x	
HRQoL and health status ^o		x			x			
PD biomarkers assessment ^q		x						

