## **2.2.2 Collection of Health-Related Quality-of-Life and Health Status Data**

At specified visits, patients will complete health-related quality-of-life (HRQoL), health status, and satisfaction/preference questionnaires on a tablet device that will remain at study sites. The instructions for completing the patient-reported outcome (PRO) questionnaires electronically will be provided by the investigator staff during the Week 1 visit at the site. The data will be transmitted automatically after entry to a centralized secure database at the vendor.

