#### **2.3.1.1 Efficacy Period**

The start of the efficacy period for each individual patient is defined as the first day when there is data in the BMQ. For patients starting the study on emicizumab (Arms A and B) this is expected to coincide with the Week 1 visit, and the day of their first emicizumab dose. For patients who do not start the study on emicizumab (Arm C), the start of the efficacy period should coincide with the Week 1 visit.

Of note, the first day when there is data in the BMQ, includes the first day for which data is reported via the handheld device, a DCR, or the day of device activation.

A second efficacy period is defined for patients in Arm C who switch to emicizumab starting on the day of their first emicizumab dose.

For patients randomized or enrolled on emicizumab, the end of the efficacy period is defined as the date of the clinical cutoff or the date of withdrawal from the initial study period (i.e., treatment phase according to eCRF), whichever is earlier. For patients randomized to no prophylaxis (Arm C), the end of the first efficacy period is defined as the day before the first emicizumab dose or the date of withdrawal from the initial study period (i.e., treatment phase according to eCRF) or the date of the clinical cutoff if neither of the aforementioned events has taken place. For patients whose dose is up-titrated, the efficacy period on the initial dose (the initial period for patients randomized to Arms A and B; the second efficacy period, starting at first emicizumab

dose for patients randomized to Arm C) ends 1 day prior to the first day on the up-titrated dose.

For patients who withdraw from the study before reaching the Week 1 visit, the duration of the efficacy period is set to 1 day, and it starts and ends on the same day of randomization/enrollment.

For patients whose dose is up-titrated, the bleeds on the up-titrated dose are analyzed separately. The efficacy period on a given up-titrated dose (second efficacy period for patients randomized to Arms A and B; third efficacy period for patient randomized to Arm C) starts with the first day on this dose and ends on the day of the clinical cutoff or the date of withdrawal.

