### **4.5.2.4 Haem-A-QoL at 24 Weeks**

The physical health subscore of the Haem-A-QoL at 24 weeks will be analyzed using analysis of variance (ANCOVA). The model will include the treatment group together

with the baseline score and treatment by baseline interaction as covariates. As for the primary analysis, a global approach with a 3-level categorical effect for treatment (1.5 mg/kg/wk, 6 mg/kg/4wks, or no prophylaxis) will be produced for the comparisons of Arm A versus Arm C and Arm B versus Arm C.

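### In the randomized arms the baseline Haem-A-QoL and EQ-5D-5L are first collected at Week 1, and nothing requires completion before the open-label assignment is known

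*Protocol*

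**What the plan says.** **Collection.** In Protocol Appendix 1-A, the row "HRQoL and health status (EQ-5D-5L) ^o" for Arms A and B is empty at Screening and marked at Weeks 1, 13, 25 and 49. The Arm C row "HRQoL and health status ^o" is also empty at Screening, with marks at Weeks 1 and 13 before the switch. SAP 2.2.2 agrees: instructions for the electronic questionnaires "will be provided by the investigator staff during the Week 1 visit at the site". On order, footnote o of Appendix 1-A says only: "The questionnaires should be completed by the patient or their caregivers at the site at the start of the visit and prior to all other" visit assessments. Protocol 4.5.7 repeats this.

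**Randomization.** Protocol 4.2 describes an open-label study with central randomization of patients who meet the entry criteria at screening. Under 4.5.1, screening results are "reviewed to confirm that patients meet all eligibility criteria before enrollment and randomization". SAP 2.3.1.1 provides for dropouts in between: "For patients who withdraw from the study before reaching the Week 1 visit, the duration of the efficacy period is set to 1 day", dated to the day of randomization or enrollment. SAP 4.2.5 counts an Arm C patient in the first safety population only if there was a Week 1 visit.

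**Use of the score.** SAP 4.5.2 places Haem-A-QoL physical health at 24 weeks (A versus C, then B versus C) at the end of the alpha-controlled hierarchy. SAP 4.5.2.4 analyzes it by ANCOVA with the baseline score and a treatment-by-baseline interaction. SAP 4.5.2.5 applies the same model, outside the hierarchy, to the Haem-A-QoL total score and to the EQ-5D-5L index and VAS. SAP 4.5.3 adds paired t-tests and counts of patients with a meaningful change. Neither document defines the HRQoL baseline.

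**The concern.** A baseline covariate should be fixed before the patient can know the assignment. Here a patient may answer the first questionnaire knowing whether emicizumab starts that day or whether another 24 weeks without prophylaxis lie ahead. Protocol 3.3 itself says that frequent bleeders may not accept a longer period on episodic therapy. If that knowledge changes the answers differently by arm, ANCOVA carries part of the difference into the treatment effect, and change from baseline and the responder counts carry all of it. At stake are the two formal Haem-A-QoL physical health tests and the supporting HRQoL results.

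**Working it through.** **1. Can the first score follow knowledge of the arm?** Week 1 is the first scheduled score in all three randomized arms. Randomization depends on eligibility at screening, and footnote e of Appendix 1-A links it only to consent. The SAP rule for patients who leave before Week 1, and its safety population definition, both presuppose randomized patients without that visit. So randomization can come first. The questionnaire-first rule protects against that day's procedures and dosing, not against knowledge of the arm. No sentence orders the questionnaire relative to randomization.

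**2. What depends on it?** The hierarchy has 2 primary tests and 8 secondary tests, so 10 in all; Haem-A-QoL physical health is tests 9 and 10.

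**3. Direction.** Protocol 4.5.7.1 states that higher scores mean poorer HRQoL, so a benefit is a negative emicizumab-minus-control difference. With a common slope,

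movement of adjusted difference = −slope × (baseline shift on emicizumab − baseline shift on control).

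Disappointed controls raise the control baseline; optimistic active patients lower the active one. Either makes the bracket negative and the movement positive, that is, against emicizumab. The opposite reporting shift would favor it.

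**4. Size.** The documents give no SD, slope or power for this endpoint; their only power figure concerns bleed rate and does not enter here. Assumptions: common slope 0.3 to 0.7, differential shift 2 to 5 points.

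- Shift 2: 0.3 × 2 = 0.6; 0.7 × 2 = 1.4 points.
- Shift 5: 0.3 × 5 = 1.5; 0.7 × 5 = 3.5 points.
- Mean change from baseline without ANCOVA moves by the full 2 to 5 points.

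The yardstick is the 10-point meaningful change for physical health in SAP 4.5.3, which is a within-patient threshold.

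**5. Effect on the test.** Further assumptions: SD 15 to 25, correlation equal to the slope, Week 25 answers unaffected, and 28 versus 14 adults (an upper bound, because adolescents complete another instrument). SE = SD × √(1 − slope²) × √(1/28 + 1/14). With SD 15 and slope 0.7 this is 15 × 0.714 × 0.327 = 3.51. A movement of 3.5 points then raises two-sided rejection under no effect from 0.05 to 0.17. Across the grid the range is 0.051 to 0.068 for a shift of 2 and 0.054 to 0.17 for a shift of 5. Under the two mechanisms in step 3, the excess rejections would favor control.

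**6. Limit of the formula.** The planned model gives each arm its own slope. At a fixed reference baseline the movement is −(slope on emicizumab × shift on emicizumab − slope on control × shift on control), which reduces to step 3 when the slopes are equal. The SAP does not state the reference value, so the figures are indicative only.

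**The case against.** The strongest reply is that the exposure is small and its sequence is inferred. Most of its parts stand.

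- **Sequence.** A reader might infer that every baseline was given with the arm known. The documents do not show that. The SAP rule is a contingency for early withdrawals, and footnote k of Appendix 1-A allows screening and Week 1 on the same day. How often randomization came first, and when patients learned their arm, is unknown.
- **Direction.** A reader might infer a bias that creates false benefit. The two most natural mechanisms work against emicizumab.
- **Recall.** The five physical health items in Protocol Appendix 3 ask about concrete symptoms over the past month. Screening lasts at most 4 weeks, so much or all of that window precedes assignment. This limits the shift without removing it.
- **Size.** The shift and slope have no source in the documents. If five items scored 0 to 4 are rescaled to 0–100 (an assumption), there are 5 × 4 = 20 steps of 100/20 = 5 points each. The upper case then needs an average differential of one full response category on one item.
- **Scope.** EQ-5D-5L and the Haem-A-QoL total score carry no alpha (SAP 2.3.2.6 and 4.5.2.5), and Haemo-QoL-SF is summarized descriptively only. The primary and other bleed endpoints do not use this score.
- **Larger exposure elsewhere.** Week 25 answers are also given with the arm known, and changing the baseline order does not address that.

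None of this supplies the missing safeguard: the plan still allows the covariate of an alpha-controlled endpoint to be measured after assignment is known.

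**Conclusion.** The concern holds in limited form. In Arms A, B and C the HRQoL baseline is guaranteed to be pre-dose but not pre-assignment. Alpha is involved only for Haem-A-QoL physical health, in tests 9 and 10 of 10; the total score, EQ-5D-5L, paired t-tests and responder counts share the weakness without formal error control. Under the stated assumptions (common slope 0.3 to 0.7, differential shift 2 to 5 points) the adjusted difference moves by about 0.6 to 3.5 points. The true size is unknown, and past-month recall probably keeps it toward the lower end. The documents do not support reading this as a threat to the primary result or as bias in favor of emicizumab. It is a cheap improvement in collection order, with a reporting remedy where the order can no longer change.

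**What to change.** 1. **Protocol Appendix 1-A, Arms A, B and C:** require Haem-A-QoL, Haemo-QoL-SF and EQ-5D-5L to be completed before the IxRS randomization call, either at Screening or on the Week 1 day with randomization only after the answers are saved.
2. **SAP 4.5.2.4, 4.5.2.5 and 4.5.3:** define the HRQoL baseline as the last score before randomization.
3. **Patients already randomized without such a score:** keep Week 1 as baseline, since the new definition alone would leave them with none. Report how many Week 1 questionnaires followed randomization, show baseline means by arm, and add a sensitivity comparison of Week 25 scores without baseline adjustment. Protocol Appendices 2-A to 2-C say that PK, biomarker and antibody sampling in these arms stopped in March 2021, which suggests that this part matters most now.

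**Cost.** One schedule change, one definition and a few outputs; the site tablet already exists. A Screening baseline may be up to 4 weeks before the first dose, and some patients who fail screening will complete questionnaires. A baseline shift cannot affect the unadjusted comparison, but that comparison is less precise: under the slopes assumed above its standard error is 1/√(1 − 0.3²) = 1.05 to 1/√(1 − 0.7²) = 1.40 times the adjusted one, so it should support the ANCOVA and not replace it.
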